4.3. Dose Modification

The starting dose of [1-¹³C]-pyruvate will be 0.43 ± 0.05 mL/kg body weight (250 mM [1-¹³C]-pyruvate). If we encounter a DLT at this dose (which seems unlikely since it has been well tolerated in safety studies elsewhere), we will decrease dose to 0.28 mL/kg.

The choice whether or not to use the [1-¹³C]-pyruvate and/or gadolinium MRI contrast agent is made at Protocol Director's discretion. If the investigator chooses to forego gadolinium contrast (due to concerns of gadolinium accumulation or other concerns), the second MRI brain scan may be skipped.

5. STUDY PROCEDURES

Healthy volunteers (Arm 1 of the study) will be recruited via an IRB-approved e-mail that refers them to the clinical research coordinator or research team. Eligible patients for arm 2 will be invited to participate at any time during their course of CNS malignancy treatment. Generally, arm 2 patients will be recruited during a regular clinic visit.

If the patient signs the informed consent form and agrees to participate, the following screening procedures will be performed within 14 days prior to Day 1:

- Collect demographics
- Measure vital signs (heart rate, temperature, blood pressure), height and weight
- Serum chemistry blood test
- Serum pregnancy test, if woman of childbearing potential
- Electrocardiogram (ECG)

On Day 1, MRI and MRSI will be performed in the Richard M. Lucas Center for Imaging at Stanford University. Production of hyperpolarized [1-¹³C]-pyruvate will be coordinated with imaging schedule such that MRSI begins within 1 minute of hyperpolarized [1-¹³C]-pyruvate administration. Each subject will undergo the following procedures:

- Measure vital signs
- MRI scan of brain, 45 min acquisition time using standard non-contrast clinical brain collection setup
- Administration of hyperpolarized [1-¹³C]-pyruvate (250 mM, 0.43 ± 0.05 mL/kg body weight) IV injection at a rate of 5 mL/sec followed by a 20 mL saline flush at 5 mL/sec (on average 30-40 seconds)
- MRSI scan of brain, 3 min acquisition on a 3T MRI scanner equipped with both 1HF and ¹³C RF coils.
- MRI scan of brain, 10 min acquisition time using standard Gadolinium-enhanced contrast clinical brain collection. Gadolinium contrast agent may or may not be administered at the discretion of the Protocol Director. Gadolinium will not be used for Arm 1 Healthy Volunteers.
- Within 10 min after the conclusion of image collection:
 - Measure vital signs
 - Collect any adverse events and monitor injection site
- At least once more 20-45 minutes after the conclusion of image collection:
 - Measure vital signs
 - Collect any adverse events and monitor injection site
- 1 to 5 hours post pyruvate administration:
 - Measure vital signs
 - ECG
 - Collect any adverse events and monitor injection site

Between Day 2 and 4, subjects will be contacted by phone or at an in-person clinic visit to collect any adverse events.

Once initial imaging is completed, patients will be followed as expected by standard of care. Patients are free to enroll in other studies.

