2.6. Study Design

This is an open-label, two-armed study of 5 healthy volunteers and 10 patients with known CNS malignancy.

- Arm 1: n = 5 healthy volunteers
- Arm 2: n = 10 patients with known CNS malignancy

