3. PARTICIPANT SELECTION AND ENROLLMENT PROCEDURES

3.1. Inclusion Criteria

- 3.1.1.** (Arm 2 patients with known CNS malignancy only) Patients with a known diagnosis of CNS malignancy, including metastases, with known enhancement on MR who are otherwise eligible to undergo MRI.
- 3.1.2.** At least 18 years old.
- 3.1.3.** eGFR $> 30 \text{ ml/min}$.
- 3.1.4.** (Arm 2 patients with known CNS malignancy only) No allergy to gadolinium.
- 3.1.5.** Ability to understand and the willingness to sign a written informed consent document.

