3.2. Exclusion Criteria

- 3.2.1.** Refusal to have an IV placed for injection.
- 3.2.2.** Acute major illness (e.g., unstable angina, etc.) or other condition that makes participation unsafe, per the investigator's judgement.
- 3.2.3.** Total Bilirubin $> 1.5 \times \text{ULN}$; AST/ALT $> 2.5 \times \text{ULN}$; GGT $> 2.5 \times \text{ULN}$.
- 3.2.4.** Pregnant or breast-feeding.
- 3.2.5.** Cardiovascular risk, including:
 - Poorly controlled hypertension, defined as either systolic > 170 or diastolic > 110 .
 - Congestive heart failure
 - Myocardial infarction within the past year
 - QT prolongation, defined as pretreatment QTc $> 440 \text{ msec}$ in males or $> 460 \text{ msec}$ in females
- 3.2.6.** (Arm 1 Healthy volunteers only) Undergoing active treatment for malignancy

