6. STUDY CALENDAR

	Pre-Study (Within 14 Days of Day 1)	Day 1	Day 2 (+2 days)
Informed consent	X		
Demographics	X		
Vital signs	X	X ^f	
Height	X		
Weight	X		
Serum chemistry ^a	X		
ECG	X	X ^e	
Pregnancy test	X ^b		
Non-contrast enhanced MRI ^c		X	
[1-¹³C]-pyruvate IV injection		X	
MRSI		X	
Contrast enhanced MRI ^d		X	
AE evaluation		X	X

a: GFR., Total bilirubin, SGOT[AST], SGPT[ALT], GGT.
 b: Women of childbearing potential only
 c: Before [1-¹³C]-pyruvate IV injection and MRSI
 d: After [1-¹³C]-pyruvate IV injection and MRSI. Arm 1 Healthy Volunteers will not receive contrast
 e: Within 1-5 hours post [1-¹³C]-pyruvate IV injection
 f: Collect on Day 1: at baseline prior to non-contrast MRI; within 10 min after the conclusion of the image collection, 20-45 min after the conclusion of image collection; and 1-5 hours post [1-¹³C]-pyruvate IV injection

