Appendix A: Inclusion/Exclusion Criteria Checklist

*All subject files must include supporting documentation to confirm subject eligibility. The method of confirmation can include, but is not limited to, laboratory test results, radiology test results, subject self-report, and medical record review.

Inclusion Criteria (From IRB approved protocol)	Yes	No	Not Applicable	Supporting Documentation*
1. (Arm 2 patients with known CNS malignancy only) Patients with a known diagnosis of CNS malignancy, including metastases, with known enhancement on MR who are otherwise eligible to undergo MRI				
2. At least 18 years old				
3. eGFR > 30 ml/min				
4. (Arm 2 patients with known CNS malignancy only) No allergy to gadolinium				
5. Ability to understand and willingness to sign a written informed consent document				
Exclusion Criteria (From IRB approved protocol)				
1. Refusal to have an IV placed for injection				
2. Acute major illness (e.g., unstable angina, etc.) or other condition that makes participation unsafe, per the investigator's judgement				
3. Total Bilirubin > 1.5 x ULN; AST/ALT > 2.5 x ULN; GGT > 2.5 x ULN				
4. Pregnant or breast-feeding				
5. Cardiovascular risk, including: o Poorly controlled hypertension, defined as either systolic > 170 or diastolic > 110. o Congestive heart failure o Myocardial infarction within the past year o QT prolongation, defined as pretreatment QTc > 440 msec in males or > 460 msec in females				
6. (Arm 1 Healthy volunteers only) Undergoing active treatment for malignancy				

IV. Statement of Eligibility

This subject is [eligible / ineligible] for participation in the study.

Signature:	Date:
Printed Name:

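### The only required pregnancy test can be 14 days old at injection, with no required re-check before the agent is given

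*Combined protocol and SAP*

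**What the plan says.** Exclusion 3.2.4 reads "Pregnant or breast-feeding". In Section 5, once consent is signed, "the following screening procedures will be performed within 14 days prior to Day 1". One item on that list is "Serum pregnancy test, if woman of childbearing potential".

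The Section 6 calendar agrees. The pregnancy-test row has a single mark, in the column headed "Pre-Study (Within 14 Days of Day 1"). Its footnote limits who is tested and does not add a second test. The Day 1 and Day 2 cells in that row are empty.

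For Day 1, Section 5 lists two steps before the injection: vital signs and a non-contrast brain MRI.

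Appendix A requires that "All subject files must include supporting documentation to confirm subject eligibility". The methods it accepts include "laboratory test results, radiology test results, subject self-report, and medical record review". It sets no limit on how old a supporting result may be.

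**The concern.** Pregnancy status can change within two weeks, and a very early pregnancy that a test misses can become detectable in that time. A woman of childbearing potential could have a valid negative result at screening, satisfy every written requirement, and be pregnant when injected. The site would have followed the protocol exactly and still have exposed someone the protocol means to exclude.

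The exposure is a single injection on a known date, so the test could readily be placed close to it. Both arms are concerned. Arm 1 healthy volunteers need only be adults, and can include women of childbearing potential. Arm 2 patients may also receive gadolinium if the Protocol Director so decides.

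What is at stake is participant protection. The documents supplied give no reproductive-risk data for the agent, so I claim no size of harm. The cited Phase I study (Section 2.2) enrolled prostate cancer patients, so it cannot inform safety in pregnancy.

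**Working it through.** The plan gives no figure to reproduce here. The check is a reading of the schedule followed by a subtraction.

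**Is any pregnancy check required between screening and injection?**

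- Section 5, screening list: one serum test, up to 14 days before Day 1.
- Section 5, Day 1 list before injection: vital signs and non-contrast MRI. No pregnancy test.
- Section 6: the test is marked pre-study only, and the footnote adds no repeat.
- Section 3.1.1: Arm 2 patients must be people "who are otherwise eligible to undergo MRI". This does not apply to Arm 1, what it covers is not stated, and no pregnancy re-check is scheduled under it.
- Sections 3.1 and 3.2: no contraception requirement.
- Sections 4.1 to 4.3: no pregnancy check at preparation, release or dosing.
- Appendix A: self-report is accepted, with no age limit on results. Self-report cannot reveal a pregnancy the participant does not know about.
- Section 5, follow-up: contact between Day 2 and Day 4 comes after the exposure and includes no pregnancy test.

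The answer is no.

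**Maximum age of the test result at injection**

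Reduction = current maximum − new maximum, with the current maximum of 14 days taken from Sections 5 and 6. The 24 to 72 hour window is an assumption.

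| Timing of the test | Maximum age (days) | Reduction (days) |
|---|---|---|
| As written | 14 | – |
| Within 72 hours (assumed) | 3 | 14 − 3 = 11 |
| Within 24 hours (assumed) | 1 | 14 − 1 = 13 |
| On Day 1 | 0 | 14 − 0 = 14 |

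**Who could be concerned**

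Section 2.6 plans 5 healthy volunteers in Arm 1, and Arm 2 is "n = 10 patients with known CNS malignancy". At most 5 + 10 = 15 people receive pyruvate, and only the women of childbearing potential among them are concerned. Section 5 rules out gadolinium in Arm 1, so at most 10 could also receive it. The number of women of childbearing potential is not given, so no expected count can be calculated.

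**The case against.** The strongest case on the other side is that this is a preference and not an error. Sections 5 and 6 are consistent with each other, the documents set no shorter standard, and a site may test nearer to Day 1 if it chooses. The numbers above describe the age of a result and do not measure risk. On the agent itself, Section 4.1 describes a stable, non-radioactive label on a compound that behaves chemically as ordinary pyruvate, and Section 4.2 includes removal of the paramagnetic agent among the quality checks. Exclusion 3.2.2 allows the investigator to exclude for any unsafe condition, and Section 4.3 lets the Protocol Director withhold pyruvate, gadolinium or both. The consent pages and the Investigator's Brochure were not available and may contain contraception advice or reproductive data. Moving the test could also mean a separate blood draw, possibly an extra visit for brain-tumor patients, and the loss of an early screen.

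Much of this stands as a limit on severity. It is a design choice, the expected number affected is small, and the risk is not quantified. The description of the agent is relevant but does not establish safety in pregnancy.

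It does not remove the gap. The discretionary provisions work only if someone already suspects pregnancy, and advice in a consent form is not a test. Fourteen days is a maximum, but nothing obliges a site to test sooner. The point about an extra visit is fair for a 24 to 72 hour window. Testing on Day 1 avoids it, provided the result can be back in time.

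**Conclusion.** The concern holds. As written, exclusion 3.2.4 can rest on a result 14 days old at the only exposure, and no required test would detect a pregnancy that begins or becomes detectable in between. Re-timing shortens the maximum by 11 to 14 days. The 14 days come from the protocol, the Day 1 alternative assumes a prompt laboratory result, and the 24 to 72 hour alternative is my assumption. A later test narrows the window without closing it, because a very early pregnancy can still be missed.

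The pregnancy could also come to light in other ways, such as a participant's own report. This is a participant-safety point that should be fixed because doing so is cheap. It has no bearing on the outcome definitions, the analysis or the sample size.

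**What to change.** In Sections 5 and 6, take the serum pregnancy test for women of childbearing potential out of the 14-day screening window and place it shortly before injection. Within 24 to 72 hours is one option; Day 1 is another if the laboratory can return the result in time. Require a documented negative result before the Day 1 non-contrast MRI and agent preparation start. Syringe release is too late a point for this check, because Section 4.2 has the syringe handed over for injection at once.

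The other screening items can keep their 14-day window. Appendix A needs no change, since the dated result serves as its supporting documentation.

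The edit is one calendar row and one line of Section 5, and the number of tests stays the same. The costs are a blood draw separate from the screening chemistry, possibly an extra visit if Day 1 testing is not feasible, and an occasional late cancellation, because a positive result would surface later than it does now. The documents give no laboratory turnaround time, so the site should settle which timing is workable.

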6. STUDY CALENDAR

	Pre-Study (Within 14 Days of Day 1)	Day 1	Day 2 (+2 days)
Informed consent	X		
Demographics	X		
Vital signs	X	X ^f	
Height	X		
Weight	X		
Serum chemistry ^a	X		
ECG	X	X ^e	
Pregnancy test	X ^b		
Non-contrast enhanced MRI ^c		X	
[1-¹³C]-pyruvate IV injection		X	
MRSI		X	
Contrast enhanced MRI ^d		X	
AE evaluation		X	X

a: GFR., Total bilirubin, SGOT[AST], SGPT[ALT], GGT.
 b: Women of childbearing potential only
 c: Before [1-¹³C]-pyruvate IV injection and MRSI
 d: After [1-¹³C]-pyruvate IV injection and MRSI. Arm 1 Healthy Volunteers will not receive contrast
 e: Within 1-5 hours post [1-¹³C]-pyruvate IV injection
 f: Collect on Day 1: at baseline prior to non-contrast MRI; within 10 min after the conclusion of the image collection, 20-45 min after the conclusion of image collection; and 1-5 hours post [1-¹³C]-pyruvate IV injection

7. ADVERSE EVENTS AND REPORTING PROCEDURES

7.1. Potential Adverse Events

In the original Phase I studies with [1-¹³C]-pyruvate, no dose-limiting toxicities or toxicities deemed to be clinically significant were noted [13]. We will consider any Grade 2 or higher toxicity judged related or possibly-related to [1-¹³C]-pyruvate as significant (excluding asymptomatic lab abnormalities).

7.1.1. Stopping Rules

The study will be stopped if infection attributable to any component of the pyruvate infusion is observed. The study may resume after the necessary chemistry, manufacturing and controls (CMC) changes are made and the IND amendment is submitted to FDA and approved by IRB. In addition, the study will pause enrollment pending a safety review if two dose-limiting toxicity events (any Grade 2 or higher toxicity judged related or possibly-related to [1-¹³C]-pyruvate, excluding asymptomatic lab abnormalities) are observed.

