7.3. Adverse Event Reporting

Non serious adverse events will be reported annually to FDA via an Annual Report (████████) and to IRB via Continuing Review.

The PD (aka Principle Investigator) must immediately report within 24 hours of knowledge of event to the IND Sponsor-Investigator ([name]), any serious adverse event, whether or not considered related to study drug. SAEs of all grades will be reported to the Sponsor-Investigator using the Stanford Cancer Institute SAE CRF.

Adverse events deemed serious, unexpected (i.e. not described in the protocol, Investigator's Brochure or informed consent documents) and related to investigational agent must be reported to the IND Sponsor-Investigator by email or fax using the FDA MedWatch form 3500a within 24 hours of knowledge of event. The IND Sponsor-Investigator is responsible for deciding whether the event meets IND Safety Reporting criteria.

Events will be submitted to Sponsor-Investigator [name], at:
[name]
Professor of Radiology and Electrical Engineering (by courtesy)
[name]
Lucas Center, ██████████
[name]

[contact]
[contact]
[contact]

It will be the responsibility of the Sponsor-Investigator to provide to the FDA all information concerning significant hazards, contraindications, side effects or precautions felt significant to the safety of the investigational agent being studied. The PD is responsible for accurate and timely communication to the Sponsor-Investigator of any events reportable to FDA.

SAEs CTCAE Grade 2 and above, and all subsequent follow-up reports will be reported to the Stanford Cancer Institute Data and Safety Monitoring Committee (DSMC) using the study specific CRF regardless of the event's relatedness to the investigation. Following review by the DSMC, events meeting the IRB definition of 'Unanticipated Problem' will be reported to the IRB using eProtocol within 10 working days of DSMC review, or within 5 working days for deaths or life-threatening experiences.

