8.3. Data and Safety Monitoring Plan

During the clinical investigation, the Protocol Director will evaluate the progress of the trial, including periodic assessments of data quality and timeliness, participant recruitment, accrual and retention, participant risk versus benefit, performance of trial sites, and other factors that can affect study outcome. Monitoring of the trial will occur every 8 weeks and a record of monitoring activities will be maintained by the study team.

The Stanford Cancer Institute Data and Safety Monitoring Committee (DSMC) will audit study related activities at least annually in accordance with the DSMC SOP to determine whether the study has been conducted in accordance with the protocol, local standard operating procedures, FDA regulations, and Good Clinical Practice (GCP). This may include review of regulatory binders, case report forms, eligibility checklists, and source documents. In addition, the DSMC will regularly review serious adverse events and protocol deviations associated with the research to ensure the protection of human subjects. Results of DSMC audits will be

communicated to the IRB and the appropriate regulatory authorities at the time of continuing review, or in an expedited fashion, as needed.

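### One related non-infectious Grade 4–5 event counts as only one of the two events needed to pause enrollment, and no rule holds dosing until it is reviewed

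*Combined protocol and SAP*

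**What the plan says.** Section 7.1.1 has two triggers. The first needs one case: "The study will be stopped if infection attributable to any component of the pyruvate infusion is observed". The second needs two: "the study will pause enrollment pending a safety review if two dose-limiting toxicity events" are seen. A dose-limiting toxicity (DLT) is any toxicity of Grade 2 or higher judged related or possibly related to the agent, leaving out laboratory findings without symptoms. Grades 2, 3, 4 and 5 carry the same weight, and the reviewing body is not named.

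Section 4.3 gives the response to a DLT at the starting dose of 0.43 mL/kg: "we will decrease dose to 0.28 mL/kg". The study calendar (section 6) shows one injection per subject, so the reduction can apply only to later subjects.

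On reporting, section 7.3 says that the Protocol Director "must immediately report within 24 hours of knowledge of event" any serious adverse event to the Sponsor-Investigator. It adds that "SAEs CTCAE Grade 2 and above, and all subsequent follow-up reports will be reported to the" DSMC, with no deadline for that report or for the review. Under section 8.3, "the DSMC will regularly review serious adverse events", and the Protocol Director's ongoing evaluation includes "participant risk versus benefit".

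The Protocol Director also releases each syringe after quality control (section 4.2) and has discretion over whether the agent is used (section 4.3). For the earlier Phase I work, section 7.1 reports that "no dose-limiting toxicities or toxicities deemed to be clinically significant were noted".

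**The concern.** Safety is the only primary objective (section 1.1), this is the site's first human use of the technology (section 2.5), and five of the 15 subjects are healthy volunteers (section 2.6). A team that followed the written rules exactly could inject the next subject before anyone had reviewed a related fatal or life-threatening event.

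The written response, a smaller volume, may also miss the cause. Section 2.1 gives as one aim to establish that the local polarizing method is safe. If a severe reaction came from local preparation and not from the amount of pyruvate, a lower dose would not deal with it. The plan already reasons this way for infection: one case stops the study, and manufacturing changes come before it resumes.

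Finally, the two-event rule pauses enrollment. It does not expressly cover a subject who has consented and is in the 14-day screening window (section 5) but has not yet been injected.

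**Working it through.** The documents give no operating characteristic for the stopping rule, so there is no stated figure to reproduce. The check is a reading of the rules, followed by a small calculation of exposure.

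**1. Trace one related, non-infectious Grade 4 or 5 event that is the first DLT.**

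| Section | What follows | Mandatory hold on dosing? |
|---|---|---|
| 7.1.1, infection stop | Does not apply | No |
| 7.1.1, two-event pause | Count is 1, threshold is 2 | No |
| 4.3 | Later subjects get 0.28 mL/kg | No |
| 7.3 | Sponsor-Investigator told within 24 hours; DSMC told, no deadline | No |
| 8.3 | DSMC reviews serious events; Protocol Director weighs risk and benefit | No |
| 4.2, 4.3 | Protocol Director may decline to use or release the agent | No, discretionary |

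The rule counts events, not subjects. Two separate related toxicities in one subject, or a severe event after an earlier Grade 2 DLT, reach the threshold. The gap concerns a severe event that stands alone.

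**2. Spacing.** Section 10.7 plans 15 subjects in one year. If evenly spread, injections are 52/15 = 3.47 weeks apart.

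**3. Subjects injected before review ends.** The event follows one subject's injection, so the next comes 3.47 weeks later. The number exposed is the whole part of (review time / 3.47). Review times are assumed.

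| Review (weeks) | Review / 3.47 | Subjects exposed |
|---|---|---|
| 1 | 0.29 | 0 |
| 3 | 0.87 | 0 |
| 4 | 1.15 | 1 |
| 12 | 3.46 | 3 |

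**4. Does late onset change this?** Safety follow-up ends by Day 4, so the review could start up to 3 days (0.43 weeks) after the injection. The next injection is then 3.47 − 0.43 = 3.04 weeks away. Reviews of 1 and 3 weeks still expose nobody. Reviews of 4 and 12 weeks give (4 + 0.43)/3.47 = 1.28 and (12 + 0.43)/3.47 = 3.58, still 1 and 3.

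**5. Dose for those exposed.** 1 − 0.28/0.43 = 34.9% lower.

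**6. Is a lone severe event the likely pattern?** The documents give no rate. For an assumed per-subject rate p of related Grade 4–5 events, with independence, at most one per subject, and no other DLTs counted, P(exactly one in 15) = 15 × p × (1 − p)^14.

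| p (assumed) | Exactly one | Two or more |
|---|---|---|
| 1% | 13.0% | 1.0% |
| 2% | 22.6% | 3.5% |
| 5% | 36.6% | 17.1% |
| 10% | 34.3% | 45.1% |

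At assumed rates of 5% or below, a single event is likelier than two or more, and a single event alone triggers no pause. The table says nothing about whether such events will occur.

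**The case against.** The strongest reply is that dosing would not run on by default. The person who must report a serious event within 24 hours also decides on use of the agent and releases every syringe. Injecting the next subject would take a deliberate act by someone who knew of the event. This stands, and it makes a voluntary halt probable. It remains discretion: after one event the written instruction is a lower dose.

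The existing rule is also sensitive in other ways. It starts at Grade 2, includes possibly related events, counts events and not subjects, and forces a dose cut after one DLT. That narrows the gap without closing it for a lone severe event.

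Section 8.3 refers to a DSMC operating procedure for audits, which is not supplied. Review times or interim actions might be set there. Nothing in the supplied text says so, which is why the review times above are assumptions.

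A pause in enrollment would naturally be read to cover subjects not yet injected. With a 2-week screening window and 3.5-week spacing, the wording rarely matters for more than one subject.

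The Grade 4 cut-off is a judgement. A related Grade 3 event in a healthy volunteer would still cause no single-event pause.

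A reader might infer that up to 14 further subjects could be injected after an event in the first subject. That would need 14 × 3.47 = 48.5 weeks with no second DLT and no action by anyone informed, so it is a theoretical ceiling only. A reader might also multiply the accrual rate by the review time and conclude that a 1- or 3-week review exposes 0.29 or 0.87 of a subject. That treats the event as falling at a random moment between injections, whereas it follows one. Under even spacing the figure is zero.

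**Conclusion.** The gap is real but narrow. As written, one related or possibly related non-infectious Grade 4–5 event that is the only DLT so far requires no pause in enrollment or dosing, and the prescribed response is to continue at a dose about 35% lower. A halt is available through the Protocol Director but is not required.

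The size is none to about three further subjects for assumed reviews of 1 to 12 weeks, and none for any review completed before the next scheduled injection. This rests on even accrual. Clustered injections would raise it and slower accrual would lower it.

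The documents do not support the reading that the plan lacks safety oversight after a death, or that such an event is to be expected. Reporting and DSMC review are in place, and no DLT was noted in Phase I. No endpoint or analysis is affected. This is a cheap improvement: it makes a rule of what a careful team would probably do anyway.

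**What to change.** Make three changes in one amendment:

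- **Section 7.1.1, add:** *Enrollment and dosing will also pause pending DSMC safety review after any single Grade 4 or 5 toxicity judged related or possibly related to [1-13C]-pyruvate (excluding asymptomatic lab abnormalities). Dosing resumes on the DSMC's written decision.*
- **Section 7.1.1, two-event rule:** pause enrollment and dosing, not enrollment alone. Keep this rule for Grade 2–3 events, and keep the infection stop as it is.
- **Section 4.3, add:** a sentence saying that the dose reduction does not replace this review.

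The text cost is two sentences and two words in 7.1.1 and one sentence in 4.3. The operating cost is an occasional short pause, including for a disease-related event among the 10 Arm 2 patients that is judged possibly related. A 4-week pause (assumed) would put off about one planned injection (4/3.47 = 1.15).
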